6. STUDY TREATMENT

6.1. Investigational Product and Other Study Treatment

The term 'study treatment' is used throughout the protocol to describe any combination of products received by the subject as per the protocol design. Study treatment may therefore refer to the individual study treatments or the combination of those study treatments.

	Study Treatment				
Product name:	GSK1278863	Placebo			
Dosage form:	Tablet	Tablet			
Unit dose	5 mg and 25 mg tablet	0 mg			
strength(s)/Dosage	strengths/10 mg, 15 mg, 25 mg,	_			
level(s):	30 mg dosage levels				
Route of Administration:	Oral	Oral			
Physical description:	A round, biconvex, 10 mm white	A round, biconvex, 10 mm white film			
	film coated tablet.	coated tablet.			

All eligible subjects will discontinue their current ESA therapy and will be randomized to receive either GSK1278863 or matching placebo on a dialysis day. This should be timed such that randomization (Day 1) occurs on the date that would have been the next scheduled dose of ESA (or as close as practicable). In addition, for subjects with a three times weekly dialysis schedule, Day 1 must not occur on the first dialysis session of the week (e.g., if Monday-Wednesday-Friday schedule, the study visit cannot be on Monday). For subjects with a four to five times weekly dialysis schedule, Day 1 can be on any hemodialysis session of the week. Examples of switching are provided in the SRM.

To maintain the blind, subjects will have study treatment dispensed from three bottles of study medication. This combination of tablets will provide the appropriate dose of study medication, and will include a combination of tablet strengths, active and placebo, to correspond to the appropriate dose.

Subjects will be dispensed one tablet from each bottle (all subjects will take three tablets in total) and take with a glass of water on a dialysis day, and this should be prior to dialysis; however, on Day 1 it is acceptable for the subject to take study medication after dialysis. All study medication should be taken in the clinic **EXCEPT** prior to the PK day (Day 15 study visit), or on other days only if the Investigator and GSK Medical Monitor agree that it will not interfere with the study procedures or affect the subject's compliance

with the protocol. The study site must ensure that the date and time the subject took each dose of study treatment is documented.

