Informed Consent	Х							
Entry Criteria	Х		Х					
Physical, Medical History, Demography	Х							
HemoCue Hgb	X	X	X	X	X	X	Χ	
IVWRS Call	X	X	Х	X	X	X	Χ	X
Females Only: Serum Pregnancy Test 3		Х					Χ	X
Females Only: Estradiol and FSH (if required) 3		X						
ECG	X				X		Χ	
Vitals (Pre-dialysis and Post-dialysis) 4		X	Х	X	X	X	Χ	X
Clinical Chemistry		Х	X	X	X	X	Χ	X
Hematology		Х	Х	Х	X	Х	Χ	X
Folate and Vitamin B ₁₂	Х							
Ferritin, transferrin, total iron, UIBC	X		X		X		Χ	Χ
Pharmacokinetic/Pharmacodynamic Samples			X	X	X		X ⁵	
Blood draw for PGx			Х					
Adverse Events Assessment 7			X	Х	X	X	Χ	Χ
Review Concomitant Medications	X		X	X	X	X	Χ	X

- 1. All assessments should be done pre-dialysis except as noted.
- 2. Allowable time window of ± 2 days for all study visits, except the follow-up visit for which it is ± 3 days.
- 3. As detailed in Exclusion Criteria in Section 5.3.
- 4. Weight measured post-dialysis only & height measured at screening only.
- 5. Obtain samples as per the Day 29 visit in Table 2. If subject does not receive a dose of study medication at this early withdrawal visit, no post-dose PK/PD samples should be obtained.
- 6. Subjects who withdraw early from treatment should attend a follow-up visit 14 days ± 3 days after the last dose of study treatment.

 7. Serious adverse events are assessed from the time of consent as stated in Section 7.4.1.1.

 Table 2
 Pharmacokinetic/Pharmacodynamic Time and Events Table

PK/PD Sample	Day 1 (dose study med at clinic)	Day 15 (dose study med at home¹)	Day 29 (dose study med at clinic)
Plasma PK ²	Pre-dose	1st sample collected approx 6-10 hr post- dose on arrival. Additional sampling: 1, 2, and 3 h after this 1st sample	Pre-dose, 1, 2, and 3 h post dose
EPO & VEGF ²	Pre-dose	1st sample collected approx 6-10 h post- dose on arrival. Additional sampling: 1, 2, and 3 h after this 1st sample	Pre-dose and 3 h post dose
Hepcidin ³	Pre-dose	Single sample during visit	Single sample during visit

- 1. Subject to take their dose of study medication at home and arrive for clinic visit approx 6-10 h post-dose. Subjects may take their Day15 dose the evening prior to the Week 2 study visit to accommodate the 6-10 h PK/PD sampling window.
- 2. Sample to be collected within 30 minutes of planned collection time.
- 3. Sample can be pre- or post-GSK1278863 administration.

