8.2.2.3.2. Vital Signs

Each vital sign parameter and change from baseline for each vital sign parameters will be summarized by visit for both pre-dialysis and post-dialysis measurements. Vital sign parameters will also summarized with respect to whether the observed values are of potential clinical importance at any time on-therapy.

A plot of mean and 95% CI for systolic and diastolic blood pressure by visit will be created for both pre-dialysis and post-dialysis measurements.

A by-subject listing of vital signs for all subjects and a listing of all vital signs for subjects with any value of potential clinical importance will be produced.

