11.4.2.1. Treatment States for Laboratory Data, Vital Signs, ECG Data

For laboratory data, pre-dialysis vital signs, and ECGs, treatment state will be defined as:

Treatment State	Definition
Pre-Treatment	Date ≤ Study Treatment Start Date
On-Treatment	Study Treatment Start Date < Date ≤ Study Treatment Stop Date + 1
Post-Treatment	Date > Study Treatment Stop Date + 1

NOTES:

- If the study treatment stop date is missing then any assessment after study treatment Start Date will be considered to be On-Treatment.
- Post-dialysis vital signs measured on the "Study Treatment Start Date" will be considered to be On-Treatment.

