11.5.2. Baseline Definition & Derivations

11.5.2.1. Baseline Definitions

For Hgb the average of Hgb measured by the central lab, Quest, at Week -2 and Day 1 visits will serve as the baseline value. If an unscheduled Hgb value is taken pre-treatment then this will be slotted following the algorithm in Section 11.3.1 and Section 11.3.2.

Vital signs will be measured both pre-dialysis and post-dialysis. The baseline values for vital signs will be defined as:

Pre-dialysis baseline = vital sign value obtained pre-dialysis on Day 1

Post-dialysis baseline = vital sign value obtained post-dialysis at Week -2

Weight baseline= post-dialysis weight measured at Week -2.

Unless stated otherwise, the baseline value for all other lab parameters and ECG are defined as the last pre-treatment value observed. This is generally expected to be from the Day 1 visit (except for Folate, B12 and ECG, which are only measured at Week -4), although such values may be missing or unscheduled assessments may be performed before treatment start.

Parameter	Study Assessments Considered As Baseline			Baseline Used in Data Display
	Week -4	Week -2	Day 1 (Pre-Dose)	
Safety				
Vital Signs		X	X	See description above [1]
ECG	X			Week -4
Laboratory (clinical chemistry and hematology)		X	X	Day 1
Folate, Vitamin B12	X			Week -4
Ferritin, Transferrin, Total Iron, UIBC	X		X	Day 1
Efficacy				
Hgb		X	X	Mean (Quest) See description above
PK/PD				
PK Plasma, EPO & VEGF, Hepcidin			X	Day 1

NOTES:

- Three measurements of SBP, DBP and HR will be recorded at each study-specified visit and the mean of the replicate assessments will be used as the baseline value.

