3.28.	Safety	LB3	Summary of Chemistry Changes from Baseline Relative to the Reference Range (or with Respect to the Normal Range)	
Use normal ranges provided by Quest/Q2 as the reference ranges.
 
On-treatment assessment only
 
Generate one table for each scheduled visit, and one for “any time on-therapy”
 
See GSK IDSL Laboratory Statistical Display Standards, Section 1.2.1 for additional details.

3.29.	Safety	LB3	Summary of Hematology Changes from Baseline Relative to the Reference Range (or with Respect to the Normal Range)	
Use normal ranges provided by Quest/Q2 as the reference ranges.
 
On-treatment assessment only
 
Generate one table for each scheduled visit and one for “any time on-therapy”.
 
See GSK IDSL Laboratory Statistical Display Standards, Section 1.2.1 for additional details.

ECGs				
3.30.	Safety	EG1	Summary of ECG Findings by Visit	
3.31.	Safety	EG2	Summary of Change from Baseline in ECG Values by Visit	Include all ECG parameters collected.

Safety : Tables				
No.	Population	IDSL / TST ID / Example Shell	Title	Programming Notes
Vital Signs				
3.32.	Safety	Table 8.25	Summary of Vital Signs by Visit	Summarize both pre and post-dialysis vital signs in separate tables SBP, DBP, Heart Rate, and Weight (Weight is measured post-dialysis only)
3.33.	Safety	Table 8.26	Summary of Change from Baseline in Vital Signs by Visit	Summarize both pre and post-dialysis vital signs in separate tables SBP, DBP, Heart Rate, and Weight (Weight is measured post-dialysis only)
3.34.	Safety	Table 8.27	Summary of Vital Signs of Potential Clinical Importance at Any Time On-therapy	Summarize both pre and post-dialysis vital signs in separate tables. SBP, DBP, and Heart Rate
Hepatobiliary (Liver)				
3.35.	Safety	Example LIVER1	Summary of Liver Monitoring/Stopping Event Reporting	
3.36.	Safety	Example: LIVER10	Summary of Hepatobiliary Laboratory Abnormalities	Follow the following treatment order: Placebo, Dapro Total, 10 mg, 15 mg, 25 mg and 30 mg

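### Day 1 post-dialysis vital signs are all classed as on-treatment although the first dose may follow dialysis, which can attenuate the contrast in one descriptive safety table

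*SAP*

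**What the plan says.** The date-based definition in SAP 11.4.2.1 is introduced with "For laboratory data, pre-dialysis vital signs, and ECGs, treatment state will be defined as". Under it, anything dated on or before the treatment start date is pre-treatment, so Day 1 laboratory values, pre-dialysis vital signs and ECGs are pre-treatment. Post-dialysis vital signs get their own note: "Post-dialysis vital signs measured on the 'Study Treatment Start Date' will be considered to be On-Treatment". The note sets no condition on when the dose was taken.

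Protocol 6.1 says the dose should come before dialysis but makes an exception: "however, on Day 1 it is acceptable for the subject to take study medication after dialysis".

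The Time and Events Table (Protocol 7.1) has a row "Vitals (Pre-dialysis and Post-dialysis) 4" that is marked at Day 1, Day 15 and Day 29, among other visits. SAP 11.5.2.1 places the post-dialysis reference earlier: "Post-dialysis baseline = vital sign value obtained post-dialysis at Week -2". The Day 1 post-dialysis reading is therefore not used up as a baseline.

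SAP 8.2.2.3.2 then plans the count that depends on treatment state: "Vital sign parameters will also summarized with respect to whether the observed values are of potential clinical importance at any time on-therapy". The programming note for Table 3.34 reads "Summarize both pre and post-dialysis vital signs in separate tables", and that table covers systolic pressure, diastolic pressure and heart rate.

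**The concern.** The SAP note orders events within Day 1 by dialysis and presumes that the dose has already been taken. The Protocol does not require that order. When the dose follows dialysis and the vital signs are taken first, a drug-free reading is labelled on-treatment and enters an any-time on-therapy count.

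The problem falls on all arms alike, but that does not make it harmless. Adding the same background to each arm raises every count and moves the contrast toward no difference. The direction deserves notice because Protocol 2.1 lists avoidance of ESA-induced hypertension among the drug's potential benefits. Day 1 is also one of only three scheduled post-dialysis visits that the rule treats as on-therapy.

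**Working it through.** The plan states no figure for this rule, so there is nothing to reproduce. The check has two parts.

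**Which displays use the label**

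- Tables 3.32 and 3.33 and Figure 3.5 are by visit. The Day 15 and Day 29 results do not use the Day 1 reading.
- The pre-dialysis part of Table 3.34 is clean, because Day 1 pre-dialysis readings are pre-treatment.
- Laboratory and ECG data on Day 1 are pre-treatment.
- The post-dialysis part of Table 3.34 is exposed.

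**Size in the exposed table**

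The documents give none of these inputs, so all are assumptions:

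- p0: per-visit rate of a post-dialysis value of potential clinical importance without drug. It is taken as the placebo rate and as equal across arms on Day 1.
- p1: per-visit rate on drug.
- f: share of subjects whose Day 1 post-dialysis reading precedes the dose.
- Visits are independent within a subject.

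Counting Day 15 and Day 29 only:

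- placebo: a = 1 − (1 − p0)²
- drug: b = 1 − (1 − p1)²

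Adding drug-free Day 1 readings for a share f, with the other subjects contributing no Day 1 reading:

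- placebo: 1 − (1 − f·p0)(1 − a)
- drug: 1 − (1 − f·p0)(1 − b)

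Subtracting, the difference becomes (1 − f·p0)(b − a), so it always shrinks by the factor 1 − f·p0.

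With p0 = 10% and p1 = 20%, a = 1 − 0.9² = 19.0% and b = 1 − 0.8² = 36.0%:

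| f | Placebo | Drug | Difference (points) | Ratio |
|---|---|---|---|---|
| 0 | 19.0% | 36.0% | 17.0 | 1.89 |
| 0.1 | 1 − 0.99 × 0.81 = 19.8% | 1 − 0.99 × 0.64 = 36.6% | 16.8 | 1.85 |
| 0.5 | 1 − 0.95 × 0.81 = 23.1% | 1 − 0.95 × 0.64 = 39.2% | 16.2 | 1.70 |
| 1 | 1 − 0.90 × 0.81 = 27.1% | 1 − 0.90 × 0.64 = 42.4% | 15.3 | 1.56 |

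With p0 = 5%, p1 = 10% and f = 1:

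- Without Day 1: 9.75% v 19.0%, ratio 1.95, difference 9.25 points.
- With Day 1: 1 − 0.95³ = 14.3% v 1 − 0.95 × 0.81 = 23.1%, ratio 1.62, difference 8.8 points.

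In subjects, at the 18 per arm of Protocol 9.2, the upper-bound loss in the first scenario is 18 × (0.170 − 0.153) = 0.3 of a subject. In the second it is 18 × (0.0925 − 0.0879) = 0.1. The ratio moves more than the difference because the denominator is inflated.

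**The case against.** The strongest defence is that this is a deliberate date convention with little effect. The SAP elsewhere counts adverse events starting on the treatment start date as on-treatment and assumes that same-day medications were taken after study treatment began. A Week -2 baseline makes the Day 1 post-dialysis reading post-baseline. Including it over-counts rather than hides possible signals. Safety is descriptive, and Listings 44 and 81 give individual vital-sign data.

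Most of this stands and limits the weight of the point. It does not remove the mismatch: the convention still labels a reading on-therapy in circumstances where the Protocol permits no drug to have been taken, and no other section corrects that.

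Three stronger readings are tempting but not supported:

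- **That pre-dose readings do enter the counts.** The documents give neither the number dosed after dialysis nor whether the dose or the vital signs came first. Entry is possible, not established.
- **That the rule dilutes any drug effect on vital signs.** The stated endpoint is absolute values and changes over time, reported by visit. Those comparisons at Day 15 and Day 29 do not use the Day 1 reading.
- **That a third of on-therapy readings are drug-free.** That needs every subject to be read before dosing, and it ignores unscheduled and early-withdrawal readings.

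Independence between visits also makes the figures generous. If a subject's readings are positively correlated, an extra Day 1 reading adds fewer newly counted subjects.

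**Conclusion.** Wrong as written, minor. The SAP note and Protocol 6.1 do not fit together, and the note can place drug-free readings in the post-dialysis part of Table 3.34. The consequence is higher counts in every arm and an attenuated contrast in that one descriptive table. At the upper bound, under assumed per-visit rates of 10% v 20%, independent visits and all subjects read before dosing, the ratio goes from 1.89 to 1.56 and the difference from 17.0 to 15.3 points. With a tenth of subjects affected, the ratio is 1.85 and the difference 16.8. The true size cannot be fixed, because the share and the underlying rates are not given. The primary analysis, the by-visit vital-sign summaries, the pre-dialysis table, laboratory data and ECGs are unaffected.

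**What to change.** Amend the note in SAP 11.4.2.1 so that a Day 1 post-dialysis vital sign is on-treatment only when the recorded Day 1 dose time shows that the dose preceded the reading. Where the order cannot be established, leave that reading out of the any-time on-therapy count, or show the post-dialysis part of Table 3.34 with and without it.

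The fallback is needed. Protocol 6.1 and 7.5.1 call for the Day 1 dose time, but 7.5.1 asks for dialysis start and stop times only at Day 15 and Day 29, and 7.4.4 specifies no clock time for vital signs. Day 1 order may therefore not be recoverable for everyone.

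The cost is one SAP sentence and either a time comparison or one extra version of a table, with no Protocol change. A few readings taken shortly after a first dose may leave the count, but they stay in the by-visit table and the listings. Classifying by dose time also gives some subjects three scheduled chances to meet a threshold and others two. The version without Day 1 avoids that, since scheduled readings then come from Day 15 and Day 29 for everyone.

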11.4.2.2. Treatment States for AE Data

For adverse events (AEs), treatment state will be defined as:

Treatment State	Definition
Pre-Treatment	AE Start Date < Study Treatment Start Date
On-Treatment	If AE onset date is on or after treatment start date & on or before treatment stop date +1. Study Treatment Start Date ≤ AE Start Date ≤ Study Treatment Stop Date + 1
Post-Treatment	If AE onset date is after the treatment stop date + 1. AE Start Date > Study Treatment Stop Date + 1
Onset Time Since 1 st Dose (Days)	If Treatment Start Date > AE Onset Date = AE Onset Date - Treatment Start Date If Treatment Start Date ≤ AE Onset Date = AE Onset Date - Treatment Start Date + 1 Missing otherwise.
Onset Time Since Last Dose (Days)	If Treatment Stop Date + 1 ≤ AE onset date: AE onset date – treatment stop date + 1 If Treatment Stop Date + 1 > AE onset date: AE onset date – treatment stop date Missing otherwise.
Duration (Days)	AE Resolution Date/AE End Date – AE Onset Date + 1

NOTES:

- If the study treatment stop date is missing then any AEs with a start date on or after study treatment start date will be considered to be On-Treatment.
- In the case of a completely missing AE start date, the event will be considered to have started on-treatment unless an end date for the AE is provided which is before start of investigational product; in such a case the AE is assigned as pre-treatment.

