9.4.3.2. Adverse Events

All AE data will be summarized, sorted by the system organ class and preferred term assigned by MedDRA, and presented by treatment group. The following summaries will be provided:

- All AEs (details for all AEs will be listed)
- Serious AEs
- AEs leading to discontinuation of study drug / withdrawal from study
- Treatment-related AEs
- AEs of special interest as defined in Section 7.4.1.2

Graphical displays will include incidence of most frequent AEs and AEs of special interest.

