6.2.6. Exposure and Treatment Compliance

The complete dosing experience will be listed for all subjects. The total duration of exposure (number of days on study drug), average three times a week dose and cumulative dose will be summarized by treatment group and Dapro total.

The average three times a week dose (the cumulative actual dose divided by the expected number of doses during the treatment period) is calculated for each subject first and the summary statistics for each treatment group and for Dapro Total are calculated based on the subject average TIW dose.

$$\text{Cumulative actual dose} = \sum_{\text{bottle}=1}^3 \left(\frac{\text{No. of tablets taken from each bottle} *}{\text{tablet strength (mg/tablet)}} \right)$$

Note: The tablet strengths are 5 mg or 25 mg for subjects randomized to dapro arms, and 0 mg for subjects randomized to placebo arm (unless the subject received daprodustat by mistake during the study).

For subjects who completed the 29-day treatment period, the expected number of doses during the treatment period is 13. For subjects who permanently discontinued the study treatment and/or withdrew from the study, the expected number of doses during the treatment period will be calculated in the same way as the calculation of the expected cumulative number of tablets for each bottle described below for compliance calculation.

For each subject “Days on study drug” will be calculated as Last Dose Date – First Dose Date +1.

A summary and a listing of study medication compliance will be produced by treatment group.

For each bottle, the compliance will be calculated for the whole study treatment period as the percentage of the cumulative number of tablets taken $[100 * (\text{cumulative number of tablets taken}) / (\text{expected cumulative number of tablets for the subject's treatment duration})]$. For subjects who completed the 29-day treatment period, the expected cumulative number of tablets should be 13. For subjects who were permanently discontinued study treatment or early withdrew from the study, following algorithm will be used to calculate the “expected cumulative number of tablets” taken from each bottle during the treatment period:

1. Determine the expected “dose day”, where “dose day” is defined as days since the first dose date. (i.e. dosing date – first dose date +1)

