 - a. For a subject who receives dialysis 3-5 times per week and starts dosing on Monday or Tuesday, the expected dose days are: 1, 3, 5, 8, 10, 12, 15, 17, 19, 22, 24, 26, and 29.
 - b. For a subject who receives dialysis 3-5 times per week and starts dosing on Wednesday or Thursday, the expected dose days are: 1, 3, 6, 8, 10, 13, 15, 17, 20, 22, 24, 27, and 29.
 - c. For a subject who receives dialysis 3-5 times per week and starts dosing on Friday or Saturday, the expected dose days are: 1, 4, 6, 8, 11, 13, 15, 18, 20, 22, 25, 27, and 29.
2. Determine the “expected cumulative number of tablets” by comparing the last dose day (last dose date – first dose date +1) with the expected dose days. For example, for a subject who received dialysis 3 times per week and started dosing on Wednesday, if the subject’s last dose day is day 7, then the expected cumulative number of tablets taken from a bottle should be 3 (because the last dose was administered before the fourth dose day); if the subject’s last dose day is day 8, then the expected cumulative number of tablets taken from a bottle should be 4 (because the last dose was administered on the fourth dose day).
3. For all other situations which is not covered in step “1” (i.e. a subject who does not receive dialysis 3-5 times per week and/or does not start dosing on Monday – Saturday), the following formula will be used to estimate the “expected cumulative number of tablets” taken from each bottle during the treatment period:

$$\text{Expected cumulative number of tablets} = \text{round}((i - 1) * 3/7, 1) + 1$$

Where “i” is the “last dose day”.

Overall compliance for a subject is categorized as follows: >0% and <80% if compliance for at least one bottle is <80%, 80% to 120% if compliance for all three bottles is between 80% and 120%, and >120% otherwise.

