11.6. Appendix 6: Derived and Transformed Data

11.6.1. General

Multiple Measurements at One Time Point

 • Three pre-dialysis measurements and three post-dialysis measurements of SBP, DBP and HR will be recorded at each study-specified visit. Mean of the measurements will be calculated and used in any derivation of summary statistics but if listed, all data will be presented. • After window assignment, if there are two or more values within a time window, the algorithm described in Section 11.3.2 will be followed. • Subjects having both High and Low values for Normal Ranges at any post-baseline visits for safety parameters will be counted in both the High and Low categories of “Any visit post-baseline” row of related summary tables. This will also be applicable to relevant Potential Clinical Importance summary tables.
Study Day

 • Calculated as the number of days from randomisation date : 
 • Ref Date = Missing → Study Day = Missing • Ref Date < Randomisation Date → Study Day = Ref Date – Randomisation Date • Ref Date ≥ Randomisation Date → Study Day = Ref Date – (Randomisation Date) + 1
Randomization Date

 • Date subject was randomized
Treatment Start Date

 • The date of first dose of study treatment
Treatment Stop Date

 • Calculated as the date of final dose of study treatment received. If treatment stop date is missing, then, for purposes of calculating exposure, it will be imputed using the date of last visit or the recorded date of withdrawal/completion, whichever is earlier. Note that the follow-up visit date must not be used as the date of last visit or recorded date of withdrawal/completion because this date will be off-treatment.
Study Completion/Withdrawal Date

 • Date of withdrawal for subjects withdrawing (i.e., subjects who actively withdraw or are deemed lost to follow-up) from study or date of completion of study for subjects who complete the study, as documented in the eCRF. 
 • Note: Subjects who die while on study are considered as having completed the study
Time Definitions (per GSK standard principles)

 • 1 week = 7 days • 1 month = 30.4375 days • 1 year = 365.25 days

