3.15.	Safety	Table 8.07	Summary of On-Therapy Treatment-Related Serious Adverse Events by System Organ Class	
3.16.	Safety	Table 8.07	Summary of On-Therapy Adverse Events Leading to Withdrawal/Permanent Discontinuation of Study Treatment by Overall Frequency (By System Organ Class)	
3.17.	Safety	Table 8.05	Summary of On-Therapy Adverse Events Leading to Withdrawal/Permanent Discontinuation of Study Treatment by Overall Frequency (By Preferred Term)	
3.18.	Safety	Table 8.18	Summary of On-Therapy Adverse Events of Special Interest	
AESI: Defined in PSAP Section 8.6.1.1. The identification of AESI will be based on SRT in-stream, blinded review of AEs
 
Footnotes of the shell need to be modified according to the AESI identified for this study. See RAP Section 8.2.2.1.

Safety : Tables				
No.	Population	IDSL / TST ID / Example Shell	Title	Programming Notes
3.19.	Safety	EudraCTNon-serious	Summary of Subjects and Number of Occurrences of Common On-therapy Non-Serious Adverse Events by System Organ Class and Preferred Term (with Occurrences >=5%)	Total number of subjects having any non-serious AE at or above >=5% within any treatment group
3.20.	Safety	EudraCTSAE	Summary of Subjects and Number of Occurrences of On-therapy Serious, Treatment-related Serious, Fatal Serious, and Treatment-related Fatal Serious Adverse Events by System Organ Class and Preferred Term	
Laboratory Parameters				
3.21.	Safety	Table 8.20	Summary of Chemistry by Visit	
3.22.	Safety	LB1	Summary of Chemistry Change from Baseline by Visit	Includes Baseline values
3.23.	Safety	Table 8.21	Summary of Hematology by Visit	
3.24.	Safety	LB1	Summary of Hematology Change from Baseline by Visit	Includes Baseline values
3.25.	Safety	Table 8.22	Summary of Hematology Data Outside the Reference Range	
3.26.	Safety	Table 8.23	Summary of Hematology and Chemistry Data of Potential Clinical Importance at Any Time On-Therapy	
3.27.	Safety	Table 8.23	Summary of Hematology and Chemistry Data of Potential Clinical Importance at Any Time Post-Therapy	

Safety : Tables				
No.	Population	IDSL / TST ID / Example Shell	Title	Programming Notes

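### The on-therapy AE window (last dose + 1 day) is shorter than the 2–3 day dosing interval, so some treatment-stopping AEs and all late follow-up AESIs fall outside Tables 3.16–3.18

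*SAP*

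**What the plan says.** SAP 11.4.2.2 classes an AE as on-treatment when "Study Treatment Start Date ≤ AE Start Date ≤ Study Treatment Stop Date + 1", and any later onset as post-treatment. SAP 11.6.1 defines the stop date: "Calculated as the date of final dose of study treatment received".

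SAP 6.2.6 gives three dose calendars. For a Monday or Tuesday start "the expected dose days are: 1, 3, 5, 8, 10, 12, 15, 17, 19, 22, 24, 26, and 29"; for a Wednesday or Thursday start "the expected dose days are: 1, 3, 6, 8, 10, 13, 15, 17, 20, 22, 24, 27, and 29". The Friday/Saturday calendar has the same spacing in a different order. Protocol 6.1 asks subjects to "take with a glass of water on a dialysis day, and this should be prior to dialysis" but gives no clock time.

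In SAP 11.14.8, Tables 3.16 and 3.17 summarise on-therapy AEs leading to withdrawal or permanent discontinuation, and Table 3.18 is the "Summary of On-Therapy Adverse Events of Special Interest". None has a post-therapy counterpart. Post-therapy tables exist only for all AEs (3.3, 3.5) and for serious AEs (3.13). The treatment-related tables (3.9, 3.10, 3.14, 3.15) and Listing 20 are also on-therapy only.

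Protocol 9.4.3.2 plans a summary of "AEs leading to discontinuation of study drug / withdrawal from study", and summaries of treatment-related AEs and AESIs, with no on-therapy condition. Protocol 7.4.1.1 collects AEs from Day 1 to the follow-up visit. SAP Table 1, which lists changes from the protocol's analysis plan, records only the new haemoglobin baseline.

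**The concern.** A one-day tail after the last dose covers the interval to the next dose when dosing is daily. It does not when planned doses are 2 or 3 days apart. A subject can be exactly on schedule, have an event before the next dose is due, stop because of it, and have the event labelled post-therapy. A discontinuation table exists to count that event, and here the onset date removes it.

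Incidence and severity of AEs and discontinuation for safety-related reasons are stated secondary endpoints. With about 18 randomised subjects per arm, one subject is 1/18, or about 6 percentage points of an arm's rate. Table 1.3 takes reasons for stopping treatment from the eCRF with no onset window, so it can show more AE-driven stops than Table 3.16. For AESIs the loss is wider, because Table 3.18 also excludes nearly all of the follow-up period.

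**Working it through.** **The dose calendar.** For completers the SAP states that "the expected number of doses during the treatment period is 13". Each of the three calendars in SAP 6.2.6 contains 13 days. The SAP's fallback formula gives the same: round((29 − 1) × 3/7) + 1 = 12 + 1 = 13. The worked example for a Wednesday start also reproduces: 3 doses by day 7 (days 1, 3, 6) and 4 by day 8. Each calendar has 12 gaps, eight of 2 days and four of 3 days: 8 × 2 + 4 × 3 = 28 days.

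**Which onsets fall outside.** Take an AE that starts after one dose and stops treatment before the next. The stop date is the date of the earlier dose. Let f be the share of a dose day that lies before the dose; the documents do not give it, so it is run from 0 to 1. Assume onset is uniform over the gap. On-therapy covers the dose date and the day after.

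- 2-day gap: only the pre-dose part of the next dose day is outside, f days.
- 3-day gap: the second calendar day after the dose, plus the pre-dose part of the next dose day, 1 + f days.
- All gaps: [8f + 4(1 + f)]/28 = (4 + 12f)/28.

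| AE window | f = 0 | f = 1/3 (08:00) | f = 1/2 (12:00) | f = 1 |
|---|---|---|---|---|
| Stop date + 1 (current) | 14% | 29% | 36% | 57% |
| Stop date + 2: 4f/28 | 0% | 5% | 7% | 14% |
| Stop date + 3 | 0% | 0% | 0% | 0% |

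The result is the same for all three calendars. An AE followed by even one more dose stays on-therapy, so these are shares of immediately stopping AEs only.

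**How many subjects.** Protocol 9.2 assumes at most 15% dropout among about 90 randomised subjects: 0.15 × 90 = 13.5, for all reasons. If every one were an immediately stopping AE, the number moved would be 13.5 × 0.143 = 1.9, 13.5 × 0.286 = 3.9 or 13.5 × 0.357 = 4.8 for f = 0, 1/3 and 1/2, with 13.5 × 0.571 = 7.7 at the f = 1 bound.

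**AESIs in completers.** With the last dose on Day 29, on-therapy ends on Day 30. For follow-up on Day 43, onsets on Days 31–43 are outside Table 3.18: 13/43 = 30% of the collection days. For follow-up on Day 40 or Day 46 the share is 10/40 = 25% or 16/46 = 35%.

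**The case against.** A reader might infer that a large part of the AEs that end treatment go missing. The documents do not support that. They give no AE timing and no dosing hour. In a 2-day gap every whole day before the next dose day is still on-therapy, and the part of the share above 14% rests on an assumed hour. The all-dropouts count is a ceiling, since dropout also covers haemoglobin stopping, missed dialysis sessions and subject choice (Protocol 5.6 and 5.6.1). All this stands.

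A reader might also infer that the events vanish from the report, or that the discontinuation endpoint goes unreported. Neither is so. The events are counted in Tables 3.3 and 3.5, and in 3.13 if serious. Listing 24 (AEs leading to discontinuation) and Listing 28 (AESIs) carry no on-therapy limit in their titles, and AE listings in that format show treatment state, so a mismatch can be traced. Table 1.3 reports the eCRF reason whatever the onset date.

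It can also be said that splitting AEs by treatment state is an expansion of the planned analyses, which Protocol 9.4 allows, and that the same + 1 rule applies to laboratory, pre-dialysis vital sign and ECG data (SAP 11.4.2.1). Both are fair, so this is not a serious departure from the protocol. But for discontinuation AEs and AESIs only the on-therapy half of the split is tabulated, and SAP 8.2.2.1 lists the AESI summary with no on-therapy wording, whereas Table 3.18 adds it.

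**Conclusion.** The point holds, at a modest size. The window is shorter than the planned dosing interval, and the tables built to count treatment-stopping AEs and AESIs use it with no post-therapy version. Under uniform onset and an immediate stop, at least 14% of such AEs fall outside, 29–36% at the assumed dosing hours, and never more than 57%. In this trial that means a few subjects at most. The AESI gap does not depend on those assumptions: for a Day-29 completer, Table 3.18 closes about 13 days before AE collection does.

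The events are missing from these summaries, not from the report. The sharpest remaining gap is a non-serious treatment-related AE two or more days after the last dose: Listing 23 covers only serious events, so it appears in no table or listing specific to treatment-related AEs. Whether the + 1 rule was carried over from the once-daily studies cannot be judged, since neither document states their AE window.

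**What to change.** - Remove the on-therapy restriction from Tables 3.16, 3.17 and 3.18, so that they count all such AEs from first dose to the follow-up visit, in line with Protocol 9.4.3.2. Optionally show them split by treatment state.
- For the treatment-related displays (Tables 3.9, 3.10, 3.14, 3.15 and Listing 20), either do the same or extend the on-treatment AE window in SAP 11.4.2.2 to stop date + 3 days, the longest planned gap.
- Do not rely on the + 3 window alone. It recovers every AE that starts within a planned gap and stops treatment, but for a Day-29 completer it ends on Day 32 and would leave later AESIs outside Table 3.18.

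The cost is a line or two of SAP wording and a changed filter or flag. Counts in these tables would rise slightly. If the window is extended, a footnote should say that the AE window differs from the laboratory window.
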